8.4. Subject Disposition

A subject disposition chart will be presented.

8.5. Demographics and Baseline Characteristics

Basic subject characteristics such as age, gender, height and weight etc., will be collected and described descriptively in a publication format.

8.5.1. Study characteristics

Subject characteristics

- Sex
- Age
- Iodine contrast agent dose received before investigation (during the previous 72 hrs)
- Treatment and diagnostic characteristics
- Time stamps for admission CT, follow-up DECT and study investigation
- Time of symptom onset, if available
- Thrombolysis yes/no (at least bolus)

IGT Systems	Clinical Research Protocol Next Generation X-ray Imaging System (NEXIS)	Doc ID: XCY612-130814 Rev: 01 Page 35 of 57
-------------	----------------------------------------------------------------------------	---------------------------------------------------

- Thrombectomy yes/no
- mTICI score at the end of thrombectomy procedure rated by treating neurointerventionalist
- Time from symptom onset to start of thrombolysis
- Time from symptom onset to end result of endovascular therapy (thrombectomy)

Any deviation from the planned analysis described below will be documented with justification in the final clinical report.

8.6. Primary objective

8.6.1. Ischemic stroke diagnostic accuracy

Endpoint

Accuracy of DE-CBCT ASPECTS to determine the extent and localization of ischemic stroke changes in brain tissue, using neCT ASPECTS as the reference standard.

Applicable subjects

Subjects diagnosed with ischemic stroke on CT.

Data

- ASPECTS
 - Left / Right
 - 1 to 10
 - Location - L, C, IC, I, M1, M2, M3, M4, M5, M6

Analysis

Images are evaluated by radiologists using neCT as reference standard and the ASPECTS diagnostic accuracy is defined.

Hypothesis:

$$H_0: \pi_1 \leq 0.80$$

$$H_1: \pi_1 > 0.80$$

Where π_1 is the observed ASPECTS accuracy and 0.80 is the performance goal.

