6.4. Informed consent process

Informed consent will be obtained from every subject in writing by the Investigator or his authorized designee before the clinical Research is started. The subject will be informed both orally and in writing about all aspects that are relevant to the subject's decision to participate in the trial, including the trial procedures and risks and benefits of participation in the clinical Research. The informed consent will include an explanation of the study, duration, explanation of medical record access and patient anonymity, and how their coded data may be transferred, used for publications or in submissions for reimbursement support. The informed consent form will contain language that is non-technical and understandable to the patient.

Ample time should be provided for the subject to read and understand the informed consent form and to consider participation. The informed consent will include personally dated signatures of the subject and the principal investigator or an authorized designee responsible for conducting the informed consent process. The investigator or an appropriately designated member of the study staff shall co-sign the consent form, indicating they believe the subject has understood the nature and risks of the study and, in their estimation, the subject clearly understands the scope of the consent. The investigator must inform subjects that they are in a clinical trial, apprise them of their rights as set forth in the informed consent document, and make written documentation that such a discussion took place. The subject will receive a copy of the signed informed consent and any other written information.

IGT Systems	Clinical Research Protocol Next Generation X-ray Imaging System (NEXIS)	Doc ID: XCY612-130814 Rev: 01 Page 25 of 57
-------------	----------------------------------------------------------------------------	---------------------------------------------------

If new information becomes available that might significantly affect the subject's future health and medical care, it shall be provided to the subjects in written form. If relevant, subject shall be asked to reconfirm their continuing informed consent in writing. In this trial only patients that can give informed consent themselves will be included.

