6.6.3.1. Inclusion criteria

1. The patient has signed and dated the Informed Consent Form (ICF)
2. Age \geq 50 years old
3. Clinical and radiological signs consistent with acute stroke
 - I. Patient diagnosed with ischemic stroke of the anterior circulation and not eligible for thrombectomy.
 - II. Patient diagnosed with ischemic stroke of the anterior circulation and subjected to thrombectomy.
 - III. Patient diagnosed with hemorrhagic stroke.

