8.2. Sample size justification

Statistical analyses will be performed by Karolinska University Hospital. This is a prospective, open label single centre study. A diagnostic study using DE-CBCT on confirmed acute ischemic or hemorrhagic stroke has not been done before. The sample size estimations aims to prove diagnostic quality non-inferiority compared to CT according to performance goals below.

The sample size for the primary endpoint is trait-based, using ten [10] ASPECTS regions for each subject. To evaluate the diagnostic accuracy of DE-CBCT compared to CT, it is estimated that a sample size of 137 is required to render a power of 90% (target accuracy of 0.90, performance goal lower boundary of 0.80, one-sided alpha of 0.025). For this endpoint, a minimum sample size of 14 subjects is required.

The first secondary endpoint (vessel tree visibility) is also trait-based, using eleven [11] arterial regions for each subject. To evaluate the proportion of regions rated equal or superior to CT, it is estimated that a sample size of 126 is required to render a power of 80% (target proportion of 0.90, performance goal lower boundary of 0.80, one-sided alpha of 0.0125, adjusted for multiple secondary endpoints). For this endpoint, a minimum sample size of 12 subjects is required.

IGT Systems	Clinical Research Protocol Next Generation X-ray Imaging System (NEXIS)	Doc ID: XCY612-130814 Rev: 01 Page 34 of 57
-------------	----------------------------------------------------------------------------	---------------------------------------------------

The second secondary endpoint is defined as diagnostic accuracy to determine the presence of intracranial hemorrhage, comparing DE-CBCT to CT (reference). The endpoint is subject-based and it is estimated that a sample size of 20 is required to render a power greater than 95% (target accuracy of 0.9999, performance goal lower boundary of 0.80, one-sided alpha of 0.0125, adjusted for multiple secondary endpoints). The sample size includes both subjects with hemorrhage and negative controls, preferably with 0.5 hemorrhage prevalence, with a threshold of at least a third of our subjects to have an intracranial hemorrhage. For this endpoint, a minimum sample size of 20 is required.

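### The primary success rule sets no requirement on affected regions, so what a pass means depends on the share of ASPECTS regions normal on neCT, which the plan does not give

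*Combined protocol and SAP*

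**What the plan says.** Section 8.6.1 tests H0: π1 ≤ 0.80 against H1: π1 > 0.80, where π1 "is the observed ASPECTS accuracy and 0.80 is the performance goal". It gives no formula for accuracy, only this: "Images are evaluated by radiologists using neCT as reference standard and the ASPECTS diagnostic accuracy is defined".

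Section 8.2 fixes the unit of analysis: "The sample size for the primary endpoint is trait-based, using ten [10] ASPECTS regions for each subject". The design values are "target accuracy of 0.90, performance goal lower boundary of 0.80, one-sided alpha of 0.025"; with these, "it is estimated that a sample size of 137 is required to render a power of 90" percent. It then converts regions to subjects: "For this endpoint, a minimum sample size of 14 subjects is required".

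The endpoint in 8.6.1 is meant to capture how far ischemic change extends and where it lies. Its analysis set is subjects with ischemic stroke on CT. No minimum number of abnormal regions, ASPECTS ceiling or expected ASPECTS is stated. Section 8.3 lists sensitivity, specificity, predictive values, AUC and kappa for use where they apply, but ties none of them to the primary decision.

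**The concern.** Accuracy over all regions is a weighted average of sensitivity and specificity, and the weights are the shares of abnormal and normal regions. Each subject contributes ten regions whatever the infarct size. If few regions are abnormal, specificity dominates and sensitivity hardly counts. The 0.80 goal then has no fixed meaning: it is a demanding bar when half the regions are abnormal and a weak one when a tenth are.

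At stake is what a declared success would show. Under some case mixes the primary objective could be met by a read that shows no ischemia at all, or by one that misses half of the affected regions.

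**Working it through.** **Inputs.** From 8.2 and 8.6.1: p0 = 0.80, p1 = 0.90, one-sided alpha 0.025, power 90%, ten regions per subject, 14 subjects. Assumed, because the documents do not give it: f, the share of regions normal on neCT, which equals mean neCT ASPECTS / 10.

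**1. The plan's own figure.** One-sample proportion, normal approximation:

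n = [(1.960 × √(0.8 × 0.2) + 1.282 × √(0.9 × 0.1)) / 0.10]² = [(0.784 + 0.384) / 0.10]² = 136.5, rounded up to 137.

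137 / 10 rounds up to 14 subjects, or 140 regions. Both figures reproduce, which supports reading accuracy as the plain proportion of regions read correctly.

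**2. The pass mark.** For an exact binomial test with n = 140 and p0 = 0.80, the smallest count with upper-tail probability at most 0.025 is 122, or 122/140 = 87.1%. The attained alpha is 0.0185, and the power at 0.90 is 0.894.

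**3. The all-normal read.** Accuracy = sensitivity × (1 − f) + specificity × f. With sensitivity 0 and specificity 1 this equals f. The pass probability is P(X ≥ 122), first with independent regions (as in 8.2), then with an assumed within-subject correlation of 0.2 (beta-binomial, 14 subjects of ten regions).

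| Mean neCT ASPECTS | f | Independent | Correlation 0.2 |
|---|---|---|---|
| 7 | 0.70 | <0.001 | 0.002 |
| 8 | 0.80 | 0.019 | 0.11 |
| 8.5 | 0.85 | 0.28 | 0.39 |
| 8.7 | 0.87 | 0.54 | 0.55 |
| 9 | 0.90 | 0.89 | 0.79 |
| 9.5 | 0.95 | >0.999 | 0.99 |

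The even-odds point is near f = 0.87 in both columns. At mean ASPECTS 9 the all-normal read has true accuracy 0.90, the design target, so with independent regions it passes with exactly the design power.

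**4. When a pass does require detection.** With perfect specificity, the lowest observed sensitivity that reaches the mark is (122/140 − f) / (1 − f):

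- f = 0.80: 0.0714 / 0.20 = 0.36
- f = 0.70: 0.1714 / 0.30 = 0.57
- f = 0.60: 0.2714 / 0.40 = 0.68
- f = 0.50: 0.3714 / 0.50 = 0.74

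**5. A read that misses half the affected regions.** Take sensitivity 0.50 and specificity 0.97, with independent regions:

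- f = 0.80: accuracy 0.100 + 0.776 = 0.876; passes 63% of the time
- f = 0.85: accuracy 0.075 + 0.8245 = 0.8995; passes 89%
- f = 0.90: accuracy 0.050 + 0.873 = 0.923; passes 99%

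**The case against.** Four arguments on the other side deserve weight.

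- **A majority of normal regions is not enough.** A reader might infer that an all-normal read passes whenever most regions are normal. It does not. At 80% normal it passes about 2% of the time with independent regions, within the nominal alpha, and at 70% or below essentially never. This stands, and it sets the limits of the point.
- **A high normal share is not established.** A reader might infer it from the recruitment rules: one group is "Patient diagnosed with ischemic stroke of the anterior circulation and not eligible for thrombectomy", and "In this trial only patients that can give informed consent themselves will be included". Section 2.6 adds that some early infarcts cannot be seen on neCT. Other text points the other way. Thrombectomy subjects are imaged on day 2, after a DECT done 12 to 36 hours after treatment (6.5), when infarcts may be more visible. The analysis set in 8.6.1 can be read as needing visible change on CT. Section 2.6 links manifest ischemia to less benefit from recanalization, so the non-thrombectomy group may include large infarcts as well as small ones. The documents do not settle the direction.
- **Section 8.3 already plans sensitivity and specificity.** Region-level data with locations are collected, so these measures can be computed, and an all-normal read would show sensitivity 0. This stands as far as reporting goes, but the pass decision would be unchanged.
- **This is a first-in-man proof of concept.** Sections 2.12 and 5.5 leave correlation with functional outcome to later work, so a formal pass has limited consequences. That lowers the stakes but does not make the rule informative.

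Section 8.6.1 also lists left and right as data. A reader might infer that both hemispheres are scored, which would raise the normal share. Section 8.2 says ten regions per subject, so the documents do not support that reading.

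**Conclusion.** The point holds in a conditional form. The rule in 8.6.1 asks nothing of affected regions, and its stringency depends on an unstated quantity. A pass with no detection of ischemia becomes more likely than not once about 87% or more of regions are neCT-normal (mean ASPECTS about 8.7 or higher). The chance is about 2%, 28% and 89% at mean ASPECTS 8, 8.5 and 9 with independent regions, or about 11%, 39% and 79% with correlation 0.2. At mean 7 or below the problem in this extreme form disappears. The milder form, a read with sensitivity 0.50 that passes, already appears at mean 8.

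These sizes rest on assumed values of mean ASPECTS, sensitivity, specificity and correlation, and on 140 regions with one result each. How the three readers' results are combined is not specified; it would change the probabilities but not the mechanism. The documents do not support saying that the trial will pass an uninformative read, or that it probably would. They support saying that the rule does not exclude it.

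**What to change.** Keep the 0.80 accuracy test and the sample size, and add to 8.6.1:

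(a) Region-level sensitivity and specificity against neCT are reported for the primary endpoint with subject-clustered 95% intervals.

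(b) The all-normal accuracy, meaning the share of neCT-normal regions in the analysis set, is stated beside the observed accuracy.

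(c) The primary objective is declared met only if the accuracy test passes and the lower 95% limit of sensitivity + specificity − 1 is above 0.

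An all-normal read has sensitivity + specificity − 1 = 0 + 1 − 1 = 0, so it can never satisfy (c).

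**Cost.** A few lines of SAP text and some extra analysis of data already collected. Power falls slightly when few regions are abnormal: by about 2 percentage points at mean ASPECTS 9, in a clustered simulation with assumed sensitivity 0.70, specificity 0.95 and correlation 0.2. At that mean only about 140 × 0.10 = 14 regions are abnormal, so the clustered interval will be fragile.

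**Limit.** Condition (c) removes only a read that carries no information. The read with sensitivity 0.50 and specificity 0.97 would still pass about 63%, 89% and 93% of the time at mean ASPECTS 8, 8.5 and 9 (independent regions, Wald interval). Items (a) and (b) are therefore needed to interpret a pass.

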8.7. Secondary objectives

8.7.1. Vessel tree visibility

Endpoint (1st Secondary endpoint)

Proportion of contrast-enhanced DE-CBCT rated non-inferior (i.e. equal or superior) vessel visibility compared to CTA (reference standard).

Applicable subjects

All subjects with a contrast enhanced DE-CBCT scan and diagnostic CT angiography.

Data

- Radiologist rating
 - Inferior/Equal/Superior
 - Distal ICA (dICA)
 - A1-A2
 - Lenticulostriate arteries

IGT Systems	Clinical Research Protocol Next Generation X-ray Imaging System (NEXIS)	Doc ID: XCY612-130814 Rev: 01 Page 36 of 57
-------------	----------------------------------------------------------------------------	---------------------------------------------------

- M1
- M2
- M3-M4
- Distal Vertebrales
- Basilar
- Basilar perforating branches
- AICA-PICA-SCA
- P1-P2

Analysis

Images are evaluated by radiologists using CT angiography as reference standard and the proportion of equal or superior vessel visibility rating in abovementioned vessel territories is defined.

Hypothesis:

$$\begin{aligned} H_0: \pi_2 &\leq 0.80 \\ H_1: \pi_2 &> 0.80 \end{aligned}$$

Where π_2 is the observed proportion of equal or superior vessel visibility and 0.80 is the performance goal.

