6.5. Investigational device exposure and comparators

As per clinic standard, patients with suspected ischemic stroke are evaluated with neCT, mCTA and CTP upon admission. Patients arriving from another hospital with a confirmed LVO can optionally be imaged with only neCT and CTP. Also, as per clinic standard, ischemic stroke patients treated in any way (thrombolysis and/or thrombectomy) undergoes DECT 12-36 hours after treatment to assess the presence and extent of hemorrhage and ischemia. Patients diagnosed with hemorrhagic stroke will typically be evaluated with neCT and mCTA/CTA upon admission.

This study will investigate the performance of DE-CBCT in comparison to regular neCT/mCTA/CTA/CTP imaging at admission and subsequent DECT (DECT only for subjects in 3.I and 3.II). Table 3 provides an overview of the devices each subject is exposed to depending on inclusion criterion.

IGT Systems	Clinical Research Protocol	Doc ID: XCY612-130814 Rev: 01 Page 26 of 57
	Next Generation X-ray Imaging System (NEXIS)	

	Day 1	Day 2						
Inclusion criterion	Standard imaging (CT-based)	Iodine contrast eligibility test	DE-CBCT w/o contrast agent	DE-CBCT w contrast agent	Iodine contrast eligibility test	Standard imaging (DECT)	DE-CBCT w/o contrast agent	DE-CBCT w contrast agent
3.I	X	X	X	X ¹	X	X ²	X	X ¹
3.II	X				X	X	X	X ¹
3.III	X	X	X	X ¹				

Table 3. Overview of the devices the subject is exposed to depending on inclusion criterion. Timeline: left to right.

¹ No iodine contrast agent will be administered if deemed ineligible

² Only if subject has been treated with thrombolysis

Italics depicts standard diagnostic protocol

Subjects presenting with acute stroke will be evaluated by the physician in accordance with the institutional practice, to establish an appropriate treatment plan based on the subject's medical condition and available diagnostic screening procedures prior to recruitment in the Study. The 3rd inclusion criterion will define the investigational device exposure for the subjects:

3.I subjects will be imaged with DE-CBCT without and with contrast agent day 1 after standard diagnostic CT imaging. If subject is still hospitalized at Karolinska on day 2, an additional DE-CBCT without and with contrast agent will be made.

3.II subjects will be imaged with DE-CBCT without and with contrast agent day 2 directly after their standard diagnostic DECT scan.

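### Vessel visibility (8.7.1): territories seen on neither scan count as successes, and in 3.II the CTA and the DE-CBCT lie on opposite sides of the thrombectomy

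*Combined protocol and SAP*

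**What the plan says.** Section 8.7.1 rates each territory on one relative scale, "Inferior/Equal/Superior", against CTA. The analysis is that "the proportion of equal or superior vessel visibility rating in abovementioned vessel territories is defined". The null hypothesis is a proportion of at most 0.80. The 11 territories run from the distal ICA to very small vessels: the lenticulostriate arteries and "Basilar perforating branches". There is no level for a territory that cannot be seen and no rule for handling one. The analysis set is every subject with a contrast DE-CBCT and a diagnostic CT angiography, so 3.II is included.

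Section 6.5 places CT angiography in the admission work-up. For the thrombectomy group it says: "3.II subjects will be imaged with DE-CBCT without and with contrast agent day 2 directly after their standard diagnostic DECT scan". Tables 1 and 3 schedule no CTA on day 2. Section 8.1 has the readers view both scans together for this endpoint.

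Section 8.2 sizes the endpoint by region, "using eleven [11] arterial regions for each subject": "it is estimated that a sample size of 126 is required to render a power of 80"%, with "target proportion of 0.90, performance goal lower boundary of 0.80, one-sided alpha of 0.0125, adjusted for multiple secondary endpoints". It concludes: "For this endpoint, a minimum sample size of 12 subjects is required".

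**The concern.** Two features let a territory count as a success without evidence about the detector.

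- **Scale.** If neither scan shows a territory, the only rating that fits is *equal*, which is a success. The small perforating vessels are the most plausible cases. Sections 8.8.5 and 8.9.2 do record whether a structure can be separated or visualised at all. The hypothesis-tested endpoint does not.
- **Timing in 3.II.** The CTA shows the vessels with the occlusion in place, and the DE-CBCT shows them after treatment meant to reopen the artery. Section 2.11.2 cites 71% recanalization at 24 hours. A reopened vessel may look better on DE-CBCT because of the thrombectomy. mTICI is collected (8.5.1) but plays no part in this analysis.

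At stake is what a pass would mean. The endpoint has its own hypothesis, performance goal and multiplicity-adjusted alpha, so it will be read as evidence that DE-CBCT shows vessels at least as well as CTA. The planned form also cannot show afterwards how many successes were uninformative.

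**Working it through.** **Inputs.** From 8.2: target 0.90, goal 0.80, one-sided alpha 0.0125, 126 regions, 11 regions per subject, 12 subjects. From 8.7.1: success means equal or superior, over all territories. Not in the documents: the number of automatic successes, called *m* below, which is assumed.

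**1. The plan's own figure.** For an exact one-sample binomial test, take the smallest pass mark r with P(X ≥ r | n, 0.80) ≤ 0.0125; power is P(X ≥ r | n, 0.90).

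- n = 126: r = 111, alpha 0.0118, power 0.81. This is the smallest n with at least 80% power, so the stated figure reproduces.
- 126 / 11 = 11.45, hence 12 subjects.
- 12 × 11 = 132 regions: r = 116, alpha 0.0121, power 0.83.

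**2. Effect of automatic successes.** If m of the 132 regions are certain successes, a pass needs 116 − m successes in the other 132 − m. With regions independent, as the plan treats them, and a true rate of 0.80 in those others, the chance of passing is P(X ≥ 116 − m | 132 − m, 0.80):

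| m | Example | Needed | Chance of passing |
|---|---|---|---|
| 0 | none | 116/132 | 1.2% |
| 4 | 4 subjects × 1 | 112/128 | 1.8% |
| 8 | 4 subjects × 2 | 108/124 | 2.7% |
| 12 | one per subject | 104/120 | 3.9% |
| 24 | two per subject | 92/108 | 10.7% |

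**3. What 0.80 overall then requires.** The overall proportion is exactly 0.80 when the rate in the remaining regions is (0.80 × 132 − m) / (132 − m). For m = 12 this is 93.6/120 = 0.780; for m = 24 it is 81.6/108 = 0.756.

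**4. Power if those regions leave the denominator.** Exact test, alpha 0.0125, true rate 0.90, 12 subjects:

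- 132 regions, pass mark 116: power 0.83
- 120 regions, pass mark 106: power 0.78
- 108 regions, pass mark 96: power 0.72

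**The case against.** Several points on the other side are sound.

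- **The stated test is not miscalibrated.** A reader might infer that the type I error is inflated. It is not. The null hypothesis concerns the proportion over all listed territories, and under it the error is 1.2%. The larger figures answer a different question: how often the trial passes when the rate in the remaining territories is only 0.80.
- **The size is unknown.** A reader might assume three or four automatic successes in every subject, which the same formula puts at 25% and 48%. The documents do not support this. Only two of the listed territories are obvious candidates, nothing says that CTA misses them, and the thrombectomy effect cannot arise in 3.I or 3.III.
- **A treated territory is not automatically superior.** The list in 8.7.1 has no left/right split, so after a one-sided occlusion the other side is still there to be compared. Admission imaging is normally multiphase CTA, which may show vessels beyond an occlusion. Transferred patients may have no on-site CTA, and without a diagnostic CTA they are outside the analysis set. Re-occlusion or distal emboli could produce inferior ratings.
- **Removing every territory not seen on CTA would overcorrect.** It would discard territories that only DE-CBCT shows, which can be genuine superiority.

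These points limit the size and shape the remedy. They do not supply a rule for territories seen on neither scan, and they do not make the two 3.II scans contemporaneous. Since thrombectomy is meant to reopen vessels, the expected net direction in 3.II is still towards success.

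**Conclusion.** The point holds as a question of what the endpoint measures, and the change is a cheap improvement. Territories seen on neither scan count in favour of DE-CBCT although they are uninformative. In 3.II, treatment between the scans can also favour it, though not strictly in one direction. The test of the all-territory proportion keeps its nominal error, but its meaning is diluted. The chance of passing with a rate of only 0.80 in the remaining territories rises from 1.2% to 1.8–2.7% with 4 to 8 automatic successes in total, 3.9% with 12 and 10.7% with 24. This rests on 12 subjects, independent regions and an assumed count that the documents do not give.

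**What to change.** In 8.7.1:

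1. Add a rating *not visible on either scan*. Take these territories out of the main denominator and report their number by territory.
2. Keep territories seen only on DE-CBCT as *superior*.
3. Prespecify a sensitivity analysis without 3.II subjects. Leaving out only their treated-side anterior territories is an alternative, but side must then be recorded in the rating. The thrombus field in 8.8.4 records side but combines M1 and M2, which 8.7.1 rates separately, so it cannot define territories beyond the occlusion.
4. Report the all-territory result as supportive.

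**Cost.** One more rating option and a few lines of analysis text. Section 8.1 has the images rated after the intervention, so no patient procedure changes. The real cost is power: with 12 subjects it falls below the stated 80% at 120 or 108 regions. Section 8.2 should restate power for the expected number of assessable regions. For example, 14 contrast subjects give 14 × 10 = 140 regions (power 0.84) or 14 × 9 = 126 (power 0.81). Exact power does not rise smoothly with n: 13 × 10 = 130 regions gives only 0.77. A range should therefore be shown.
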